Figure 3-2. Cohort 6 Visit Schema.....38

PROTOCOL SYNOPSIS

Gilead Sciences, Inc.
[name]
[name]

Study Title: A Phase 1b, Randomized, Blinded, Placebo-Controlled Dose-Escalation Study of the Safety and Biological Activity of GS-9620 in HIV-1 Infected, Virologically Suppressed Adults

IND Number: 122452
EudraCT Number: Not Applicable
Clinical Trials.gov Identifier: NCT02858401

Study Centers Planned: Multiple centers in North America

Objectives: The primary objectives are:

- To evaluate the safety and tolerability of escalating, multiple doses of GS-9620 in HIV-1 infected virologically suppressed adults on antiretroviral therapy (ART)
- To evaluate the virologic effect of GS-9620 as measured by changes in plasma HIV-1 RNA

The secondary objectives are:

- To evaluate the plasma pharmacokinetics (PK) of GS-9620
- To evaluate the pharmacodynamics (PD) of GS-9620 as measured by changes in interferon-stimulated genes (ISGs) and serum cytokines in whole blood compared to placebo
- To evaluate effects of GS-9620 on whole blood immune cell activation (T cell, B cell, NK cell)

The exploratory objectives are:

█ [REDACTED]

█ [REDACTED]

[REDACTED]

Study Design:

This is a randomized, double-blinded, multi-cohort dose-escalation study with dose cohorts: Cohort 1 (1 mg Dose), Cohort 2 (2 mg Dose), Cohort 3 (4 mg Dose), Cohort 4 (6 mg Dose), Cohort 5 (8 mg Dose), Cohort 6 (three administrations of 10 mg Dose, followed by seven administrations of 12 mg Dose; SEC review of the 10mg safety data will be required prior to dose escalating to 12mg), and optional Cohort 7 CCI

[REDACTED]

Two additional optional adaptive cohorts, Cohort 8 CCI and Cohort 9 CCI

[REDACTED]

[REDACTED]

For each cohort, eight subjects will be randomized in a 6:2 ratio to receive GS-9620 or placebo.

Subjects will receive a total of either 6 doses in Cohorts 1 to 3, 10 doses in Cohorts 4 to 6, CCI of their assigned study treatment administered once every other week. For all subjects in Cohort 6, Dose 4 (Day 43) will

occur after SEC review has been completed. If dose escalation is approved by the SEC, subjects in Cohort 6 will receive 12 mg of GS-9620 or placebo from Doses 4 to 10; if dose escalation is not approved by the SEC, subjects will continue receiving 10 mg of GS-9620 or placebo from Doses 4 to 10.

Enrollment will initially be opened for Cohort 1 only. A SEC will review study progress, safety and virology results of enrolled subjects. After all subjects in a cohort have received at least three doses (Cohorts 1 to 3, and 6) or five doses (Cohorts 4 and 5), the SEC will review safety data from that cohort, including adverse events (AEs) and clinical laboratory results (including plasma HIV-1 RNA) before approving the next dose escalation. CCI

A cohort may be suspended if
≥ 2 out of 6 subjects receiving GS-9620 experience one or more dose-limiting toxicities (DLTs) considered related to study drug.

- Number of Subjects Planned: Approximately up to 72 subjects total (6 GS-9620; 2 placebo per cohort)
- Subjects who discontinue study participation before completion of dosing for reasons other than study treatment-related AEs may be replaced
- Target Population: HIV-1 infected male and non-pregnant, non-lactating female adults who have been virologically suppressed (HIV-1 RNA < 50 copies/mL) on ART for ≥ 12 consecutive months prior to screening
- Main Eligibility Criteria:
- HIV-1 infection
 - Aged ≥ 18 years at Pre-Baseline/Day -13
 - On antiretroviral (ARV) treatment for ≥ 12 consecutive months prior to Pre-Baseline/Day -13
 - The following agents are allowed as part of the current ARV regimen: NRTIs, raltegravir, dolutegravir, rilpivirine, and maraviroc
 - The following agents are NOT allowed as part of the current ARV regimen: HIV protease inhibitors (including low dose ritonavir), cobicistat-containing regimens, elvitegravir, efavirenz, etravirine, and nevirapine

- A change in ARV regimen ≥ 45 days prior to Baseline/Day 1 for reasons other than virologic failure (eg, tolerability, simplification, drug-drug interaction profile) is allowed
- Plasma HIV-1 RNA < 50 copies/mL at screening
- Documented plasma HIV-1 RNA levels < 50 copies/mL (according to the local assay being used) for ≥ 12 months preceding the screening visit (measured at least twice using a licensed assay with a lower limit of quantitation of at least 40 copies/mL)
 - Unconfirmed virologic elevations of ≥ 50 copies/mL (transient detectable viremia, or “blip”) prior to screening are acceptable. (If the lower limit of detection of the local HIV-1 RNA assay is < 50 copies/mL, the plasma HIV-1 RNA level cannot exceed 50 copies/mL on two consecutive HIV-1 RNA tests)
 - If ARV regimen is changed ≥ 45 days prior to Pre-Baseline/Day -13, plasma HIV-1 RNA < 50 copies/mL at Pre-baseline/Day -13 visit is required.
- No documented history of resistance to any components of the current ARV regimen
- Availability of a fully active alternative ARV regimen, in the opinion of the Investigator, in the event of discontinuation of the current ARV regimen with development of resistance.
- Hgb ≥ 11.5 g/dL (males) or ≥ 11 g/dL (females)
- WBC ≥ 4000 cells/ μ L
- Platelets $\geq 150,000$ /mL
- ANC ≥ 1500 cells/ μ L
- CD4 count ≥ 400 cells/ μ L
- Albumin ≥ 3.9 g/dL
- ALT and AST $\leq 2 \times$ ULN
- Estimated glomerular filtration rate ≥ 60 mL/min
- No autoimmune disease (e.g. lupus erythematosus, rheumatoid arthritis, inflammatory bowel disease, sarcoidosis, moderate or severe psoriasis)
- No evidence of current HBV infection
 - Positive anti-HBs antibody and negative HBsAg results are acceptable

- No evidence of current HCV infection
 - Positive anti-HCV antibody and negative HCV PCR results are acceptable
- No documented history of pre-ART CD4 nadir < 200 cells/μL
 - Unknown pre-ART CD4 nadir is acceptable
- No history of Class C AIDS-Defining Condition
 - No acute febrile illness within 35 days prior to Pre-Baseline/Day -13

Study Visits and
Procedures:

Visit Schedule:

The main study phase consists of a screening period of up to 35 days, a pre-treatment period of 14 Days (from Day -13 to Day 1), treatment period of 71 days (Cohorts 1 to 3), 127 days (Cohorts 4 to 6), CCI and a follow-up period of 30 days after the last dose of study drug is taken. Enrolled subjects will undergo the following scheduled study visits:

Cohort 1 to Cohort 3

Day -13 (**Pre-Baseline**)

Day 1 (**Baseline/Dose 1**), Day 3, Day 5, Day 8, Day 11

Day 15 (**Dose 2**), Day 17, Day 19, Day 22, Day 25

Day 29 (**Dose 3**), Day 31, Day 33, Day 36, Day 39

Day 43 (**Dose 4**), Day 45, Day 47, Day 50, Day 53

Day 57 (**Dose 5**), Day 59, Day 61, Day 64, Day 67

Day 71 (**Dose 6**), Day 73, Day 75, Day 78, Day 81

Day 101 (**End of Study**)

Cohort 4

Day -13 (**Pre-Baseline**)

Day 1 (**Baseline/Dose 1**), Day 2, Day 3, Day 8

Day 15 (**Dose 2**), Day 22

Day 29 (**Dose 3**), Day 36

Day 43 (**Dose 4**), Day 50

Day 57 (**Dose 5**), Day 58, Day 59, Day 64

Day 71 (**Dose 6**), Day 78

Day 85 (**Dose 7**), Day 92

Day 99 (**Dose 8**), Day 106
Day 113 (**Dose 9**), Day 120
Day 127 (**Dose 10**), Day 128, Day 129, Day 134
Day 157 (**End of Study**)

Cohorts 5 to 9

Day -13 (**Pre-Baseline**)
Day 1 (**Baseline/Dose 1**), Day 2, Day 3, Day 8
Day 15 (**Dose 2**), Day 22
Day 29 (**Dose 3**), Day 31, Day 36
Day 43 (**Dose 4**), Day 45, Day 50
Day 57 (**Dose 5**), Day 58, Day 59, Day 64
Day 71 (**Dose 6**), Day 73, Day 78
Day 85 (**Dose 7**), Day 87, Day 92
Day 99 (**Dose 8**), Day 101, Day 106
Day 113 (**Dose 9**), Day 115, Day 120
Day 127 (**Dose 10**), Day 128, Day 129, Day 134
Day 157 (**End of Study**)

Subjects who prematurely discontinue study drug will be required to complete an Early Study Drug Discontinuation Visit within 30 days after their last dose of study treatment.

The Pre-Baseline/Day -13 visit has an allowable window of ± 3 days.

- Visits scheduled for 2, 4, 7, or 10 days after a Dosing visit, **except for Day 2, 3, 58, 59, 128 and 129** have an allowable window of ± 1 day.

The Day 101 and 157 visits have an allowable window of ± 3 days.

Non-dosing visits may occur at the investigator site or at other location agreed by the subject and mobile nurse vendor.

Screening Procedures:

Screening procedures include: complete physical examination, vital signs, height, weight, medical history (including route and estimated duration of HIV infection, pre-ART viral set point, and complete ARV history), HIV-1 RNA, ARV trough PK, hematology, serum chemistry, serum pregnancy test, urinalysis, HBV and HCV serologies, eGFR, and electrocardiogram (ECG). Pre-ART CD4 nadir and historical genotype will be collected if available.

In order to establish eligibility, Investigators may repeat screening procedures or laboratory assessments for subjects who have an acute illness or abnormal laboratory value that is expected to resolve without sequelae within the screening window.

On-Study Procedures:

Dosing:

For **Cohorts 1 to 3**, dosing visits will occur at Day 1, Day 15, Day 29, Day 43, Day 57, and Day 71. For **Cohorts 4 to 9**, dosing visits will occur at Day 1, Day 15, Day 29, Day 43, Day 57, Day 71, Day 85, Day 99, Day 113 and Day 127. CCI

For **Cohorts 1 to 4**, subjects will fast for at least 2 hours before dosing. For **Cohorts 5 to 8**, subjects will fast overnight (at least 8 hours) before dosing. CCI

The Investigator will verify the subject's continued eligibility for dosing at post-Baseline dosing visits, including the absence of dose-limiting toxicities (DLTs) and (for females of childbearing potential) a negative urine pregnancy test, prior to dosing. All doses will be directly administered by blinded site staff. Subjects will fast for 2 hours after dosing for all cohorts. After Dose 1, subjects will remain on site for 12 hours after dosing for safety assessment and phlebotomy.

Safety:

Solicitation of AEs and concomitant medications and symptom-directed physical examination at every visit.

Hematology, serum chemistry, and urinalysis weekly for Cohorts 1 to 3. For **Cohorts 4 to 9** these labs will be collected on dosing days, seven days post dose (starting from Dose 4), at end of study, and ESDD. For **Cohorts 6** CCI these labs will also be collected on Day 2 and two days post dose (starting from Dose 5).

CCI

Urine pregnancy test (for females of childbearing potential) prior to each dose.

Vital signs (blood pressure, pulse, respiration rate and temperature) at all dosing visits.

Subjects will be instructed to contact the site immediately if any flu-like symptoms are noted (eg, fatigue, pyrexia, chills, myalgia, joint pain or headache).

Pharmacokinetics:

Plasma GS-9620 concentrations will be collected at the following time points **for all cohorts**:

- Pre-dose (≤ 5 minutes prior to dosing), 0.5, 1, 2, 4, 6, 8, 10, and 12 hours post dose at Day 1; then one sample 48 hours post dose at Day 3
- **If the SEC approves the dose escalation to 12 mg in Cohort 6, starting from Dose 4 and onwards**, plasma GS-9620 concentrations will also be collected on Day 43 (Dose 4): Pre-dose (≤ 5 minutes prior to dosing), 0.5, 1, 2, 4, 6, 8, 10, and 12 hours post dose; then one sample 48 hours post dose at Day 45

CCI

A single trough ARV PK sample will be collected at Pre-Baseline/Day -13 (**Cohorts 1 to 3**) or at Screening, Day 29, Day 57, Day 85 and Day 99 (**Cohort 5**), or at Screening, Day 57 and Day 99 (**Cohorts 6** CCI CCI

The timing of the ARV trough collection is to be 20-24 hours following the subject's previous QD regimen dose and before next ARV dose (and, for any subject on a regimen containing a BID component, the trough collection must also occur 8-12 hours following the subject's previous dose of that BID component and before next ARV dose). These samples may be analyzed to assess interim ART adherence.

Pharmacodynamics:

Whole blood ISG mRNA panel: **For Cohorts 1 to 3**, immediately before and 2 days and 7 days after each dose of study drug, and at the end of the study (Day 101). **For Cohorts 4 to 9**, immediately before and 1 day, 2 days and 7 days after doses 1, 4 (only if Cohort 6 subjects receive 12 mg starting at Dose 4), 5 and 10. CCI

TLR7 genotyping: at Pre-Baseline/Day -13

Virology:

Plasma HIV-1 RNA: at every visit except Pre-Baseline (Day -13).

Cell-associated HIV-1 RNA/DNA (CAVR/CAVD), and plasma HIV-1 RNA by Single Copy Assay (SCA) will be collected immediately before and two days post Doses 1, 4, 6 and at end of the study (Cohort 1 to 3); immediately before and two days post Doses 1, 5, 10 and at end of the study (Cohorts 4 to 9). CCI

HIV-1 reservoir measurements: at Pre-Baseline/Day -13 and at the end of the study (Cohorts 4 to 9). CCI

Immunology:

Peripheral blood immune cell numbers for T/B/NK/pDC/mDC including: CD4 and CD8 populations, CD4/CD8 ratio, CD4% and lymphocyte activation (T, B and NK cells) by flow cytometry will be collected immediately before and two days post Doses 1, 3, and 6 (Cohorts 1 to 3), and immediately before, one and two days post Doses 1, 5 and 10 (Cohorts 4 to 9). CCI

FoxP3+ Treg cells by flow cytometry will be collected immediately before Doses 1, 3, and 6 (Cohorts 1 to 3), and immediately before Doses 1, 5 and 10 (Cohort 4 to 9). CCI

Changes in the levels of antiviral cytokines and inflammatory markers by chemiluminescence: immediately before and 2 days and 7 days after each dose, and at the end of the study (Cohorts 1 to 3). For subjects in Cohorts 4 to 9, immediately before, post dose days 1, 2 and 7 after Doses 1, 4 (only if Cohort 6 subjects receive 12 mg at Dose 4), 5 and 10. CCI

PBMC Intracellular cytokine staining (ICS) for Treg cells: immediately before and 2 days after Doses 1 and 6 for subjects in Cohorts 1 to 3.

HIV-specific T-cell responses by ELISPOT will be collected at Pre-Baseline/Day -13, immediately before Dose 6 and at the end of study for subjects in **Cohorts 1 to 3**.

For subjects in Cohorts 4 to 9, HIV-specific polyfunctional T cell Intracellular Cytokine Staining (ICS) and HIV-specific T-cell responses by ELISPOT will be collected at Pre-Baseline/Day -13 and at the end of the study. **CCI**

Stool sample will be obtained for microbiome analysis. (Day 1 and Day 157 for **Cohorts 5 to 9**). **CCI**

CCI

Additional End of Study Procedures:

Symptom-directed physical examination, review of AEs and concomitant medications, weight, eGFR, hematology, serum chemistry, urinalysis, urine pregnancy test (for females of childbearing potential, if not performed within the previous 30 days).

Early Study Drug Discontinuation Visit Procedures:

Symptom-directed physical examination, review of AEs and concomitant medications, weight, eGFR, HIV-1 RNA, hematology, serum chemistry, whole blood ISG mRNA panel, serum cytokine/soluble biomarker studies, urinalysis, urine pregnancy test.

Procedure Definitions and Specifications:

HIV-1 RNA will be performed by a licensed assay with a lower limit of quantitation of at least 20 copies/mL.

Hematology panel includes: complete blood count (CBC) with differential and platelets, CD4+ cell count, CD8+ cell count, CD4/CD8 ratio, and CD4%.

Serum chemistry panel includes: alkaline phosphatase, AST, ALT, total and direct bilirubin, total protein, albumin, bicarbonate, BUN, calcium, chloride, creatinine, glucose, phosphate, magnesium, potassium, sodium, CPK, and uric acid.

Urinalysis includes dipstick. **Serum and urine pregnancy tests** are performed only on female subjects of childbearing potential.

Phlebotomy volume limits will be maintained in accordance with American Red Cross blood donation guidelines, which limit blood donation to 473 mL every 56 days. Subjects will undergo periodic phlebotomy over a 149-day period and will provide no more than 473 mL every 56 days. Subjects will be prohibited from blood donation in excess of that required for clinical care within 30 days prior to screening and 30 days after study ends.

Study Treatment:

Investigational Medicinal Products:	GS-9620: 1 mg, 2 mg, 4 mg, 6 mg (administered as three 2 mg tablets), 8 mg (administered as two 4 mg tablets), 10 mg (administered as five 2 mg tablets), 12 mg (administered as six 2 mg tablets, or three 4 mg tablets) dose administered orally once every other week.
Reference Treatment:	Placebo-to-match GS-9620, administered orally once every other week.
Duration of Treatment:	The treatment duration is 71 days (Cohorts 1 to 3), 127 days (Cohorts 4 to 6), CCI [REDACTED]
Other Treatment:	Subjects will continue their existing ARV regimen (as currently prescribed and supplied) for the duration of study participation.

Criteria for Evaluation:

Safety: AEs and clinical laboratory tests will be collected at every visit and summarized through Day 101 or Day 157 (30 days after the last dose of GS-9620 or placebo).

The following are DLTs:

- ALT elevation defined as:
 - $ALT \geq 10 \times ULN$ **OR**
 - confirmed ALT elevation (i.e. grade shift or $2 \times$ previous value) with evidence of worsened hepatic function (e.g. total bilirubin > 2 mg/dL above Baseline, serum albumin > 1 g/dL decrease from Baseline)
- A confirmed \geq Grade 3 AE considered by the investigator to be study drug-related

- A confirmed \geq Grade 3 lab abnormality considered by the investigator to be study drug-related and clinically significant
- A persistent (≥ 72 hours) \geq Grade 2 flu-like symptom (eg pyrexia, fatigue, myalgia, arthralgia, headache, chills) considered by the investigator to be study drug-related
- A post-dose increase in plasma HIV-1 RNA that fails to resolve to < 50 copies/mL within 10 days in Cohorts 1 to 3
- A post-dose increase in plasma HIV-1 RNA that fails to resolve to < 200 copies/mL within 10 days in Cohorts 4 to 9

The Investigator will notify the SEC within 24 hours of any DLT. The SEC may unblind the treatment assignment for a subject experiencing a DLT.

Study drug dosing for a subject may be discontinued if the subject receives GS-9620 and experiences one or more DLTs considered to be related to study drug.

A Dose Cohort may be discontinued if ≥ 2 out of 6 subjects receiving GS-9620 experience one or more DLTs considered related to study drug.

Statistical Methods:

Safety:

To evaluate overall safety, the incidences of treatment-emergent AEs and treatment-emergent laboratory abnormalities will be summarized by treatment group.

The proportion of subjects in each treatment group with an AE leading to premature discontinuation of study drug and proportion of subjects with serious adverse events (SAEs) will be summarized by treatment group.

Virology:

The change in plasma HIV-1 RNA and the incidence of detectable plasma HIV-1 RNA at each visit will be summarized by treatment group.

The change in plasma HIV-1 RNA SCA from pre-dose to 2 days post-dose may be explored.

The change in cell (PBMC) associated HIV-1 RNA from pre-dose to 2 days post-dose may be explored.

The change in HIV-1 reservoir measured by cell (PBMC) associated HIV-1 DNA from pre-dose to 2 days post-dose, and in Cohorts 4 to 9 by use of secondary assays using stored PBMC samples may be explored

- PK: Exposure parameters of GS-9620 will be summarized using descriptive statistics by active treatment.
- PD: The change from baseline in the levels of serum cytokines will be summarized using descriptive statistics by treatment group. The post-baseline change and fold induction in mRNA for ISGs will be summarized using descriptive statistics by treatment group.
- Immunology: The post-baseline change in peripheral blood immune cell numbers for T/B/NK/pDC/mDC including: CD4 and CD8 populations, CD4/CD8 ratio, CD4 % and lymphocyte activation (T, B and NK cells) will be summarized using descriptive statistics by treatment group.
- The post-baseline change in magnitude and poly-functionality (Cohorts 4 to 9) of the HIV-1-specific T cell immune response may be explored.
- TLR7 genotype may be reported and its association with key pharmacodynamic and virologic parameters may be explored.
- Sample Size: This is an exploratory study to characterize the safety and efficacy of GS-9620; therefore, no power calculation was performed. Sample size is determined based on empirical considerations. A total of up to 54 subjects (6 per cohort) receiving GS-9620 will provide a reasonable preliminary assessment of safety.

This study will be conducted in accordance with the guidelines of Good Clinical Practice (GCP) including archiving of essential documents.

GLOSSARY OF ABBREVIATIONS AND DEFINITION OF TERMS

°C	degree(s) Celsius
°F	degree(s) Fahrenheit
ACTG	AIDS Clinical Trials Group
AE	adverse event
AIDS	Acquired Immune Deficiency Syndrome
ALT	alanine aminotransferase (SGPT)
ANOVA	analysis of variance
ART	antiretroviral therapy
AST	aspartate aminotransferase (SGOT)
ATI	analytical treatment interruption
AUC _{0-t}	area under the plasma concentration-time curve from zero
AUC _{24h}	area under the plasma concentration-time curve in 24 hours
AUC _{tau}	area under the plasma concentration versus time curve over the dosing interval (tau)
BID	bis in die (two-or twice-a-day)
BLQ	below the limit of quantitation
BUN	blood urea nitrogen
CAVR/CAVD	Cell-associated HIV-1 RNA/DNA
CBC	complete blood count
CDC	Center for Disease Control and Prevention
CFR	Code of Federal Regulations (United States)
C _{last}	last observed quantifiable concentration of the drug
CL _{cr}	creatinine clearance
C _{max}	maximum observed concentration of drug
CNS	central nervous system
CPK	creatine phosphokinase (= creatine kinase, CK)
CSR	clinical study report
C _{tau}	observed drug concentration at the end of the dosing interval (tau)
CYP3A	cytochrome P450
dL	deciliter(s)
DLT	dose-limiting toxicities
DNA	deoxyribonucleic acid
DTG	dolutegravir
EC	ethics committee
EC ₅₀	50% effective inhibitory concentration
ECG	Electrocardiogram
EDC	Electronic data capture
eCRF	electronic case report form(s)

eGFR	estimated glomerular filtration rate
ESDD	Early Study Drug Discontinuation
EudraCT	European Union Drug Regulating Authorities Clinical Trials
FDA	Food and Drug Administration (United States)
FSH	Follicle stimulating hormone
FTC	emtricitabine
ET	early termination
G	Gram
GCP	Good Clinical Practice (Guidelines)
GGT	gamma-glutamyl transferase (= gamma-glutamyl transpeptidase, GGTP)
GSI	Gilead Sciences, Inc.
HBV	hepatitis B virus
HCV	hepatitis C virus
HBsAg	hepatitis B virus surface antigen
HLT	high level term
HLGT	high level group term
HPF	high-power field
HIV	human immunodeficiency virus
hr	Hour
ICH	International Conference on Harmonization
ICS	intracellular cytokine staining
IC ₅₀	50% inhibitory concentration
IEC	Institutional Ethics Committee
IFN	Interferon
IFN- α	interferon-alpha
IND	Investigational New Drug (Application)
IP-10	interferon γ -inducible protein-10
IRB	Institutional Review Board
ISGs	interferon-inducible genes
IUD	intrauterine device
IU	international unit
kg	Kilogram
LLN	lower limit of the normal range
LLOD	lower limit of detection
LLT	lower level term
LRA	latency reversal agents
MAD	multiple ascending dose
MedDRA	Medical Dictionary for Regulatory Activities; MedDRA [®]
mg	Milligram
μ g	Microgram

min	Minute
mDC	conventional (myeloid) dendritic cell
mL	Milliliter
mRNA	messenger ribonucleic acid
NK	natural killer (cell)
NDA	New Drug Application
NOAEL	no observed adverse effect level
NRTI	Nucleoside Reverse-Transcriptase Inhibitors
PEG	pegylated interferon
PBMC	peripheral blood mononucleated cell
PCR	polymerase chain reaction
PD	pharmacodynamics(s)
pDC	plasmacytoid dendritic cell
PK	pharmacokinetic(s)
POC	Proof of concept
PT	prothrombin time
PT	preferred term
PVE	Pharmacovigilance and Epidemiology, Gilead Sciences
PXR	pregnane X receptor
QD	quaque die (one- or once-a-day)
QOD	every other day (dosing)
qPCR	quantitative PCR
RBC	red blood cell (count)
RNA	ribonucleic acid
SAD	single ascending dose
SADR	serious adverse drug reaction
SAE	serious adverse event
SCA	single copy assay
SD	standard deviation
SEC	Safety Evaluation Committee
SIV	Simian immunodeficiency virus
SOC	System Organ Class
SUSAR	Suspected Unexpected Serious Adverse Reaction
T _{1/2}	estimate of the terminal elimination half-life of the drug, calculated by dividing the natural log of 2 by the terminal elimination rate constant (λ_z)
Th1/Th2/Th17	T helper cells (1, 2, 17)
Tr1	Type 1 T regulatory cells
T _{last}	time (observed time point) of C _{last}
T _{max}	time (observed time point) of C _{max}
T _{reg}	T regulatory (cells)

TBD	to be determined
TFV	tenofovir
TLR	toll-like receptor
ULN	upper limit of the normal range
US	United States
USA	United States of America
vs	versus
WHO	World Health Organization
wt	weight
λ_z	terminal elimination rate constant, estimated by linear regression of the terminal elimination phase of the concentration of drug versus time curve

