 - 6.4.2.4.2. Hematology profile: complete blood count (CBC) with differential and platelet count (**Days 59 and 129 only**)
 - 6.4.2.4.3. Plasma HIV-1 RNA (TaqMan® v2.0)
 - 6.4.2.4.4. Serum for cytokine/soluble biomarker studies
 - 6.4.2.4.5. Whole blood ISG mRNA panel
 - 6.4.2.4.6. Cell-associated HIV-1 RNA/DNA with stored PBMC
 - 6.4.2.4.7. Plasma HIV-1 RNA Single Copy Assay with stored plasma
 - 6.4.2.4.8. Whole blood for immune cell activation (T, B, NK)
 - 6.4.2.4.9. GS-9620 plasma pharmacokinetic assessment (Day 3 only)

6.4.3. Treatment Assessments on Non Dosing Days 8, 22, 36, 50, 64, 78, 92, 106, 120 and 134

All study visits are to be scheduled relative to the Baseline/Day 1 visit. Study visits on Days 8, 22, 36, 50, 64, 78, 92, 106, 120 and 134 are to be completed within \pm 1 day of the protocol specified visit date. The following procedures will be performed:

- 6.4.3.1. Review of AEs and changes in concomitant medications
- 6.4.3.2. Symptom-directed physical examination as needed
- 6.4.3.3. Urine collection for urinalysis (**Days 50, 64, 78, 92, 120 and 134 only**)

- 6.4.3.4. Blood sample collection for the following laboratory analyses:
 - 6.4.3.4.1. Chemistry profile: alkaline phosphatase, AST, ALT, total bilirubin, direct and indirect bilirubin, total protein, albumin, CPK, bicarbonate, BUN, calcium, chloride, creatinine, glucose, phosphorus, magnesium, potassium, sodium, uric acid **(Days 50, 64, 78, 92, 120 and 134 only)**
 - 6.4.3.4.2. Hematology profile: complete blood count (CBC) with differential and platelet count **(Days 50, 64, 78, 92, 120 and 134 only)**
 - 6.4.3.4.3. Plasma HIV-1 RNA (TaqMan[®] v2.0)
 - 6.4.3.4.4. CD4+ cell count **(Days 50, 64, 78, 92, 120 and 134)**
 - 6.4.3.4.4.1. CD8+ cell count, CD4/CD8 ratio and CD4 % **(Days 50, 64, 78, 92, 120 and 134 for Cohorts 5 to 9 only)**
 - 6.4.3.4.5. Serum for cytokine/soluble biomarker studies **(Days 50, 64 and 134 only)**
 - 6.4.3.4.6. Whole blood ISG mRNA panel **(Days 50, 64 and 134 only)**
- 6.4.4. Treatment Assessments on Dosing Days 15, 29, 43, 57, 71, 85, 99, 113 and 127**

Subjects are to arrive in a fasting state for the Dosing Days 15, 29, 43, 57, 71, 85, 99, 113 and 127 and to follow fasting and food/liquids consumption requirement shown in 1. Initiation of the treatment with the study drug must take place in the clinic and will be administered by blinded study staff.

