6.4.4.9. In-Clinic Dosing

6.4.5. Treatment Assessments on Non Dosing Days 31, 45, 73, 87, 101 and 115 (For Cohorts 5 to 9 only)

All study visits are to be scheduled relative to the Baseline/Day 1 visit. Study visits on Day 31, Day 45, Day 73, Day 87, Day 101 and Day 115 Day are to be completed within ± 1 day of the protocol specified visit date. The following procedures will be performed:

- 6.4.5.1. Review of AEs and changes in concomitant medication
- 6.4.5.2. Symptom-directed physical examination as needed
- 6.4.5.3. Urine collection for urinalysis (**Days 73, 87, 101 and 115 only**)
- 6.4.5.4. Blood sample collection for the following laboratory analyses:
 - 6.4.5.4.1. Chemistry profile: alkaline phosphatase, AST, ALT, total bilirubin, direct and indirect bilirubin, total protein, albumin, CPK, bicarbonate, BUN, calcium, chloride, creatinine, glucose, phosphorus, magnesium, potassium, sodium, uric acid (**Days 73, 87, 101 and 115 only**)
 - 6.4.5.4.2. Hematology profile: complete blood count (CBC) with differential and platelet count (**Days 73, 87, 101 and 115 only**)
 - 6.4.5.4.3. Plasma HIV-1 RNA (TaqMan[®] v2.0)
 - 6.4.5.4.4. Serum for cytokine/soluble biomarker studies (**Day 45**, only if the SEC approves the dose escalation to 12 mg in Cohort 6 starting from Dose 4)
 - 6.4.5.4.5. Whole blood ISG mRNA panel (**Day 45**, only if the SEC approves the dose escalation to 12 mg in Cohort 6 starting from Dose 4)

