8.9. Safety Evaluation Committee

A Safety Evaluation Committee (SEC) will review study progress, virology and safety of enrolled subjects. The SEC will consist of members not directly involved with the conduct of the study. After all subjects in a cohort have received at least three doses (Cohorts 1 to 3, and 6) or five doses (Cohorts 4 and 5), the SEC will review safety data from that cohort, including adverse events, clinical laboratory results, and plasma HIV-1 RNA, before approving opening of enrollment in the next cohort. For Cohort 6, SEC will confer once all subjects have completed 3 doses of 10 mg GS-9620, and recommend whether or not subjects may proceed with a dose escalation to 12 mg starting with Dose 4. CCI

A cohort may be suspended if ≥ 2 out of 6 subjects receiving GS-9620 experience one or more DLTs considered related to study drug. Please refer to the SEC Charter for additional details.

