VAS Questionnaire			X					X					X										X				X								
Plasma HIV-1 RNA	X		X	X	X	X	X	X	X	X	X	X	X	X	X	X	X	X	X	X	X	X	X	X	X	X	X	X	X	X	X	X	X	X	X

Study Procedure ^a	Screen ^b	Pre-Baseline	Dose ^c	Day 1 Post L	Day 2 Post L	Day 7 Post L	Dose	Day 7 Post L	Dose	Day 2 Post L	Day 2 Post L	Day 7 PdDosi	Dose ^d	Day 2 Post L	Day 7 Post L	Dose	Day 1 Post L	Day 2 Post L	Day 7 Post L	Dose	Day 2 Post L	Day 7 Post L	Dose	Day 2 Post L	Day 7 Post L	Dose	Day 2 Post L	Day 7 Post L	Dose	Day 2 Post L	Day 7 Post L	Dose 1	Day 1 Post L	Day 2 Post L	Day 7 Post L	End of Stu	ESDI	
	Day 48	Day 13	Baseline Day	Day	Day	Day	Day 1	Day 2	Day 2	Day 3	Day 3	Day 3	Day 4	Day 4	Day 5	Day 5	Day 5	Day 5	Day 6	Day 7	Day 7	Day 7	Day 8	Day 8	Day 9	Day 9	Day 9	Day 10	Day 10	Day 11	Day 11	Day 11	Day 12	Day 12	Day 12	Day 12	Day 13	Day 15
Cell associated HIV-1 RNA/DNA (CAVR/CAVD) with stored PBMCs			X ^o	X											X ^o		X																X ^o	X		X		
Plasma HIV-1 RNA Single Copy Assay with stored plasma			X ^o	X											X ^o		X																X ^o	X		X		
PBMC – ELISPOT ¹		X																																		X		
Whole blood – immune cell activation			X ^o	X	X										X ^o	X	X																X ^o	X	X			
Whole blood - flow FoxP3+ Treg			X ^o												X ^o																		X ^o					
T cell ICS ⁱ		X																																			X	
HIV-1 Reservoir measurement ⁱ		X																																			X	
CCI																																						
Review DLTs to confirm dosing can proceed							X	X		X					X							X					X					X						
In-Clinic Dosing ¹			X				X	X		X					X							X					X					X						

b Evaluation to be completed within 35 days prior to Pre-Baseline/Day -13
 c Subjects should be administered study drug after Baseline/Day 1 visit assessments (except for post-dose intensive PK)

- d Dose 4 (**Cohort 6 only**) cannot occur until SEC completes review of the safety data from all subjects' first three doses (GS-9620 10 mg dose). If the GS-9620 10mg dose is found to be safe, Dose 4 and subsequent Doses (5-10) will escalate to GS-9620 12 mg. If dose escalation is not approved by the SEC, subjects will continue receiving 10 mg of GS-9620 or placebo from Doses 4 to 10
- e All study visits are to be scheduled relative to the Baseline/Day 1 visit date
- f Collect ART history for at least 12 months; Pre-ARV viral set point, pre-ARV CD4 nadir and historical genotype will be collected if available
- g Urogenital/anorectal exams may be performed at discretion of the Investigator

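### Cohort 6 moves from 10 mg to 12 mg on a review of three doses, but scheduled hematology, chemistry and urinalysis cover only two of them

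*Protocol*

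**What the plan says.** **The decision.** Protocol 8.9 states for Cohort 6 that the "SEC will confer once all subjects have completed 3 doses of 10 mg GS-9620, and recommend whether or not subjects may proceed" to 12 mg from Dose 4. Appendix 2 (Cohorts 5 to 9, footnote d) adds that Dose 4 "cannot occur until SEC completes review of the safety data" from the first three doses of all subjects. Section 6.4.4 places Dose 4 (Day 43) after completion of that review. Section 8.9 lists the material for SEC review as adverse events, clinical laboratory results and plasma HIV-1 RNA.

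**The sampling.** The synopsis (On-Study Procedures, Safety) says of hematology, chemistry and urinalysis in Cohorts 4 to 9 that "these labs will be collected on dosing days, seven days post dose (starting from Dose 4), at end of study, and ESDD". For Cohort 6 it adds that "these labs will also be collected on Day 2 and two days post dose (starting from Dose 5" onward. Section 6.4.3, which covers the 7-day visits, restricts the three panels to "Days 50, 64, 78, 92, 120 and 134 only", so Day 36 is excluded. Section 6.4.5, which covers the 2-day visits, restricts them to "Days 73, 87, 101 and 115 only", so Days 31 and 45 are excluded.

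**What does happen after Dose 3.** Visits take place on Days 31 and 36, with adverse event review, symptom-directed examination as needed and plasma HIV-1 RNA.

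**The concern.** The review rests on three doses, but the routine safety panels follow only two. The pattern of 7-day panels from Dose 4 suits Cohorts 4 and 5, whose SEC review comes after five doses. It does not suit Cohort 6, whose review comes after three.

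Two criteria for dose-limiting toxicity (DLT) in 7.6.1 depend on these panels: the ALT elevation, and the confirmed, clinically significant, drug-related laboratory abnormality of Grade 3 or higher. The decision at stake moves all Cohort 6 subjects on active drug to the highest dose in the trial. If the schedule is followed exactly, the SEC takes that decision with no routine panel bearing on either criterion after the third 10 mg dose.

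**Working it through.** No power or sample-size formula applies. The check lists the days with hematology, chemistry and urinalysis in Cohort 6, from Protocol 6.2.3 and 6.4.1 to 6.4.5, and counts them by dosing interval.

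Inputs: Doses 1 to 4 fall on Days 1, 15, 29 and 43. Panels up to Day 43 fall on Days 1, 2, 15, 29 and 43. HIV-1 RNA is taken at every visit after Pre-Baseline. The chemistry, hematology and urinalysis rows of the Protocol's own Cohorts 5 to 9 table do not appear in the public text. The SAP copy (Appendix 2) agrees with section 6.4: the Day 31 and Day 36 cells are blank.

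| 10 mg dose | Panels after it, before the SEC decision | Days since that dose | HIV-1 RNA before the next dosing visit |
|---|---|---|---|
| Dose 1 (Day 1) | Days 2 and 15 | 1 and 14 | Days 2, 3, 8 |
| Dose 2 (Day 15) | Day 29 | 14 | Day 22 |
| Dose 3 (Day 29) | none | not applicable | Days 31, 36 |

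- Doses covered by the three panels: 2 of 3. Doses covered by HIV-1 RNA: 3 of 3.
- In administrations: six active subjects × 3 doses = 18 doses of 10 mg, if all six complete them. Six × 1 = 6 of those 18 have no scheduled panel before the decision.

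**Day 43.** A panel is listed at this visit, before the DLT check and dosing. It would be 14 days after Dose 3, the same kind of coverage that Dose 2 gets from Day 29. But it belongs to the Dose 4 visit, which comes after the SEC review. At that visit the pre-dose cytokine and ISG samples and the intensive PK sampling already depend on whether 12 mg was approved, so the visit presupposes the decision. Section 7.6.2 also asks for repeat testing of clinically significant Grade 3 and 4 abnormalities within 3 calendar days of receipt of results. No passage describes a panel drawn ahead of a held Dose 4.

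**Other cohorts, after the dose that triggers their review:**
- Cohorts 1 to 3 (Dose 3, Day 29): chemistry on Day 36, hematology on Days 31 and 36.
- Cohorts 4 and 5 (Dose 5, Day 57): all three panels on Day 64.
- Cohort 6 (Dose 3, Day 29): none before the next dosing visit.

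**After escalation.** If 12 mg is approved, Doses 4 to 10 are seven 12 mg doses. The 2-day panels fall on Days 59, 73, 87, 101, 115 and 129, that is, after Doses 5 to 10, or six of the seven. Dose 4, the first at 12 mg, has none on Day 45. It does have a 7-day panel on Day 50.

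**Day 106.** This is the 7-day visit after Dose 8. Section 6.4.3 and the Cohort 4 table omit the panels there, although the synopsis describes 7-day panels from Dose 4 on.

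**The case against.** The strongest reply is that the review is triggered by doses received, and no passage requires a chemistry panel after each dose or after the last one. On that reading, the safety data from three doses means whatever the schedule yields. This stands to the extent that there is no flat contradiction in wording. But 8.9 names clinical laboratory results alongside HIV-1 RNA, footnote d ties the review to all three doses, and for these panels the schedule gives nothing after the third.

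A reader might infer that the SEC has no laboratory data at all after Dose 3. The documents do not support that. HIV-1 RNA is drawn on Days 31 and 36, the synopsis counts it among the clinical laboratory results, and 7.6.1 makes it a DLT criterion. A reader might also infer that laboratory toxicity could not be found. That too goes too far: symptoms can be picked up on Days 31 and 36, SAP 3.8.2 allows for unscheduled visits, and the Day 43 panel is drawn before any 12 mg dose. What is missing is routine sampling in time for the decision.

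Nor is Cohort 6 the most thinly sampled on every count. Before Dose 4 it has three post-dose chemistry panels (Days 2, 15, 29) against two in Cohorts 4 and 5 (Days 15, 29) and five in Cohorts 1 to 3 (Days 8, 15, 22, 29, 36). Nothing says that the SEC reviews in the other cohorts waited for Day 36 or Day 64; the comparison shows only that a panel was scheduled.

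**Conclusion.** The point holds for hematology, chemistry and urinalysis. The ALT and Grade 3 or higher laboratory DLT criteria are not routinely sampled between Dose 3 and the decision to escalate, and Cohort 6 is the only one of Cohorts 1 to 6 without a scheduled panel between the dose that triggers its review and the next dosing visit. The missing 2-day panel after the first 12 mg dose and the Day 106 mismatch are smaller; the latter has no bearing on the escalation decision.

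This rests on the visible text of the synopsis, 6.4.3 to 6.4.5, 8.9 and footnote d, and on the SAP's copy of the table. Figure 3-2 (the Cohort 6 visit schema) is not shown, the SEC Charter is not supplied, and some Cohort 6 text is redacted. Any of these could describe an added sample.

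**What to change.** Reconcile the passages on the review (6.4.4, 8.9 and footnote d of the Cohorts 5 to 9 table) with those on sampling (synopsis Safety paragraph, 6.4.3, 6.4.5 and the same table). The laboratory data that the SEC is said to review for the three 10 mg doses should match what is collected. The sponsor chooses how; no dose or clinical rule is proposed here. In the same edit, reconcile Day 106 in 6.4.3 and the Cohort 4 table with the synopsis, and state whether the absence of a 2-day panel after Dose 4 is intended.

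The cost is a few table cells or a sentence of text. Visits with blood draws already exist on Days 31 and 36. If samples are added, the extra volume must be checked against the limit of 473 mL per 56 days. SAP 2.1.1 describes the SEC analyses as already performed, Cohort 6 included. If so, the clinical study report should state which post-Dose-3 panels the SEC had when it decided.
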